5. ANALYSIS SETS

5.1. SAFETY POPULATION

The Safety Population, defined as all subjects who receive at least 1 dose of ALRN-6924, will be used for safety analyses and summaries of demographics and baseline characteristics.

5.2. EFFICACY EVALUABLE POPULATION

The Efficacy Evaluable Population is defined as those subjects who meet all of the following criteria:

- Received at least one dose of ALRN-6924 at a dose level at least 0.8 mg/kg per infusion.
- Have at least one post-baseline evaluation or had clinical disease progression
- Are TP53 wild type or indeterminate (as assessed by the central lab; if not assessed by central laboratory, as assessed by the local laboratory)

This population will be used for analyses of clinical activity.

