5.7.1 Dose Levels for the Dose Escalation Portion of the Study

In the Dose Escalation portion of the study, increasing dose levels of ALRN-6924 will be evaluated in cohorts of 3-6 DLT-evaluable patients per dose regimen. Patients enrolled in Cohort 1 receive ALRN-6924 at Dose Level 1 (0.16 mg/kg). Based on allometric scaling, at 0.16 mg/kg dose in humans, the predicted AUC (50 $\mu\text{g}\cdot\text{hr}/\text{mL}$) is approximately 9% of the rat AUC at STD_{10} and approximately 6% of the AUC at the monkey HNSTD as described in Section 1.4.

In the absence of DLT in >33% of DLT-evaluable patients in either DR, subsequent cohorts of 3 to 6 patients will receive escalated doses until the MTD or an OBD is established for each dose regimen.

A 2-stage dose escalation design will be employed. During the initial Stage 1 Escalation Phase, 100% dose increments will be utilized until ≥ 1 of 3 patients in a cohort experiences any Grade ≥ 2 AE that is at least possibly related to study drug. Study drug-related AEs Grade ≥ 2 occurred in DL-4A (fatigue) and in DL-3B (neutropenia). Therefore, per protocol, Stage 2 has been implemented for subsequent dose escalations starting with DL-5A and DL-4B. Dose escalation will continue using 3-patient cohorts and the modified Fibonacci sequence (i.e., 67%, 50%, 40%, 33%), until the MTD or an OBD is established. As two DLTs have occurred in DR-7A (hypotension and hepatobiliary laboratory abnormalities), there will be no further dose escalation in DR-A. A new modified infusion regimen was tested (DR-A-2) starting at dose level 7A-2 (=4.4 mg/kg body-weight). As two DLTs have occurred in DR-7A-2 (anemia and neutropenia), there will be no further escalation in DR-A-2.

Figure 9: Dose Level and Dose Regimen Schematic

The observation of DLT(s) will be used to make individual patient determinations regarding dose reductions, interruptions or discontinuation throughout the course of the trial, but DLTs occurring during Cycle 1 will be used to inform safety and tolerability assessments for dose escalation decisions.

If DLTs are observed in the first cohort, the dose will be de-escalated to Dose Level -1. If DLTs are observed at Dose Level -1, the dose will be de-escalated to Dose Level -2. If DLTs are observed at Dose Level -2, other dose levels may be considered and implemented after discussions among the Investigators and Sponsor's Medical Monitor.

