5.7.2 Dose Levels for the Expansion Portion of the Study

The EXP will enroll up to 5 distinct groups of patients with specific solid tumors and/or lymphomas to further investigate the clinical safety profile and potential efficacy of ALRN 6924 at the MTD, OBD, or an alternative dosing regimen. PTCL has been selected as one of the EXP groups to be further studied; up to 3 cohorts in PTCL may be studied in order to determine the optimal dosing regimen. Another Phase 2a EXP group will include patients with MDM2 amplified or MDM2/CDK4 co-amplified solid tumors who will receive ALRN-6924 in combination with palbociclib.

Phase 2a Expansion in PTCL

Two DLTs were observed at DL-7A (hypotension and hepatobiliary laboratory abnormalities) rendering DL-7A the maximum administered dose whereas in DL-6A, only one DLT was observed (fatigue) in six DLT-evaluable patients. Furthermore, a complete remission has been observed in a PTCL patient at DL-5A (2.1 mg/kg). Therefore, the first selected dose and schedule for the Phase 2a expansion in PTCL is

3.1 mg/kg on Days 1, 8, and 15 of a 28 day cycle (DL-6A). Alternative dosing regimens to be tested may include 2.7 mg/kg on Days 1, 4, 8, and 11 of a 21 day cycle (DR-B) and 3.1 mg/kg on Days 1, 3, and 5 of a 21 day cycle (DR-C). Six to 8 patients will be enrolled in DR-C in a run-in part and the treating investigators, along with the Medical Monitor, will review safety and tolerability through Cycle 1 prior to opening the full DR-C expansion cohort. Lower dose levels for DR-C, in 25% reductions in the starting dose, may be assessed if the safety and tolerability of 3.1 mg/kg are not acceptable. Should this occur, 6-8 patients will again be enrolled into a run-in part and the treating investigators and Medical Monitor will meet again to review all patients prior to opening the full DR-C expansion cohort. For each dose level assessed during the run-in part, the SRC will use the DLTs defined in Phase 1 as a guide for determining safety.

Phase 2a Expansion in MDM2 amplified or MDM2/CDK4 co-amplified solid tumors

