5.7.3 Intra-Patient Dose Escalation- Phase 1 Dose Escalation

A patient's dose may be increased to that of a cohort that completed the first cycle without dose-limiting toxicity in $\geq 33\%$ of DLT-evaluable patients and that has not exceeded the MTD. Intra-patient dose escalations will be allowed provided that the patient completed at least two treatment cycles and did not experience study medication-related toxicity greater than Grade 2 (except for alopecia, electrolyte disturbances responsive to correction within 24 hours, diarrhea, nausea, fatigue and vomiting that responds to standard medical care). Approval for intra-patient dose escalation must be obtained from the Medical Monitor.

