Subjects who do not have disease progression (or death) will be censored at the last known time point that the subject was progression-free. Subjects with two or more consecutive missing response assessments prior to a visit with progression (or death) will be censored at the last date of tumor assessment when the subject was known to be progression free.

- Best Overall Response (BOR) - the highest level of objective response recorded (complete response, partial response, stable disease, or progressive disease) for each subject
- Progression-free Survival (PFS), defined as the time from the date of the first dose of ALRN-6924 to the date of first evidence of objective or clinical disease progression or the date of death, due to any cause, whichever occurs first. The PFS will be calculated as follows (in months):

(date of disease progression/death - first dose date + 1)/30

Subjects who do not have disease progression (or death) will be censored at the last known time point that the subject was progression-free. Subjects with two or more consecutive missing response assessments prior to a visit with progression (or death) will be censored at the last date of tumor assessment when the subject was known to be progression free.

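### The Phase 1 efficacy set is defined by a dose ever received, so patients who started below 0.8 mg/kg enter only if they stayed on treatment long enough to be escalated

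*SAP*

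**What the plan says.** SAP 5.2 sets three conditions for the Efficacy Evaluable Population. The first is that the patient "Received at least one dose of ALRN-6924 at a dose level at least 0.8 mg/kg per infusion". The others are a post-baseline evaluation or clinical progression, and TP53 wild-type or indeterminate status. Protocol 7.6 gives the same dose condition for dose escalation. SAP 5.2 adds: "This population will be used for analyses of clinical activity".

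Protocol 5.7.3 governs how a patient moves to a higher dose: "Intra-patient dose escalations will be allowed provided that the patient completed at least two treatment cycles". It also requires that the target cohort has completed its first cycle within the DLT limit, that the patient has had no related toxicity above Grade 2 (with listed exceptions), and that the Medical Monitor approves.

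In SAP 4.2, PFS is "defined as the time from the date of the first dose of ALRN-6924" to progression or death. TTR has the same origin. DCR and BOR count assessments at any dose. SAP 3.1 tabulates everything by dose cohort within regimen, by regimen, and overall. It does not say whether dose cohort means the dose assigned or the dose received.

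**The concern.** The dose condition can be met after baseline. A patient who started at or above 0.8 mg/kg meets it on Day 1. A patient who started below meets it only by staying on treatment for two cycles or more and then being escalated. A low-dose patient who progressed and stopped at the first scan never enters.

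Two distortions follow. For DCR, BOR and ORR, the low-dose patients admitted are selected on having done well. For PFS, the selected patients also bring guaranteed time: the clock starts at their first low dose, so the wait before they qualified counts as follow-up in which they could hardly have failed and still be in the set. The SAP has no landmark, no restart of the clock at the first qualifying dose, and no sensitivity set by assigned dose. At stake is the descriptive picture of Phase 1 activity.

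**Working it through.** **Which levels start below 0.8 mg/kg.** Protocol 5.7.1 starts at 0.16 mg/kg and says "100% dose increments will be utilized until" a related Grade 2 or higher event occurs. After that it uses the "modified Fibonacci sequence (i.e., 67%, 50%, 40%, 33%), until the MTD or an OBD is established". It places the switch in Regimen A after level 4.
- Doubling gives 0.16, 0.32, 0.64 and 1.28 mg/kg for levels 1 to 4.
- Check against stated doses: 1.28 × 1.67 = 2.14 (2.1 at level 5A); 2.1 × 1.5 = 3.15 (3.1 at 6A); 3.1 × 1.4 = 4.34 (4.4 at 7A-2). All agree within 2%.
- So levels 1, 2 and 3A lie below 0.8 mg/kg and level 4A lies above. The Regimen B doses are in a figure that is not shown, so its low levels cannot be confirmed.

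**Earliest qualifying dose.** Two cycles put it at Day 2 × 28 + 1 = 57 in Regimen A and Day 2 × 21 + 1 = 43 in Regimen B. The target cohort must also have completed Cycle 1. With no gaps between 28-day cohorts, the minimum wait for level 4A is:
- from level 1: 4 × 28 = 112 days
- from level 2: 3 × 28 = 84 days
- from level 3A: 2 × 28 = 56 days

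**Link to outcome.** Protocol 6.10 places the first Regimen A scan before Cycle 3, about day 56. For solid tumors, Appendix K sets the minimum for stable disease at 5 weeks. A Regimen A solid-tumor patient without progression at that scan has therefore met disease control at a dose below the threshold before entering the set.

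**Size.** The following are assumptions, not figures from the documents: 45 patients starting at or above 0.8 mg/kg; 9 starting below (3 per level); exponential PFS with a true median of 60 days at every dose; DCR taken as progression-free past day 56; a fraction *f* of low-dose patients still progression-free at the end of their wait escalating.
- P(PFS > t) = 0.5^(t/60), which is 0.524, 0.379 and 0.274 at 56, 84 and 112 days.
- Expected number added = *f* × 3 × (0.524 + 0.379 + 0.274) = 3.53*f*.
- Pooled DCR ≈ (45 × 0.524 + 3.53*f*) / (45 + 3.53*f*). At *f* = 1 this is (23.6 + 3.5) / 48.5 = 55.8%.

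Simulated results:

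| Escalating (*f*) | Added | DCR | Median PFS (days) |
|---|---|---|---|
| none | 0 | 52% | 61 |
| 30% | 1.1 | 53% | 63 |
| 60% | 2.1 | 54% | 65 |
| 100% | 3.5 | 56% | 67 |

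If only 70% of low-dose patients meet the TP53 condition (assumed), 0.7 to 2.5 are added and DCR is 53% to 55%.

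**Low-dose rows.** If dose cohort means assigned dose, these rows hold only escalated patients. Under the model their DCR is 100% against a true 52%. Their median PFS is the wait plus 60 days: 116, 144 or 172 days for waits of 56, 84 or 112, against a true 60.

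**DCB.** This clock starts at first documented disease control, about day 56 in Regimen A. With a constant hazard and a 56-day wait, median DCB does not change. With the longer waits it rises by about 1 to 3 days.

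**The case against.** The case that this matters little has several sound parts.

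- **Stakes.** The Phase 1 primary objectives are safety, DLTs and the MTD or OBD. Analyses are descriptive, and no efficacy threshold or test depends on them. This stands. For scale, the planned Wilson interval at 23 of 45 (51%) runs from 37% to 65%, far wider than the shift.
- **Who escalated.** The documents report no intra-patient escalation, and each one needs approval. Wild-type TP53 was required only from level 4, so the TP53 condition thins the low-dose group further. This also stands and limits the size.
- **By-cohort tables.** A reader might infer that disease control at low doses is credited to the active dose rows. The documents do not support that. Patients are enrolled in cohorts and SAP 3.1 tabulates by cohort, so on the natural reading escalated patients stay in their low-dose row. Rows at 0.8 mg/kg or above are then untouched, but the regimen and overall columns are not.
- **Certainty of disease control.** A reader might infer that every patient added this way has disease control. Protocol 5.3 allows treatment past progression with agreement. In Regimen B two cycles end at day 42, before the first scan at about day 63. Being alive and on treatment is guaranteed; being progression-free is only nearly so.

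SAP 6.2 summarizes reasons for exclusion from each set. That discloses who was dropped but does not correct the estimates.

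**Conclusion.** The concern holds in limited form. As written, the set selects low-dose patients on outcome for DCR, BOR and ORR and adds guaranteed time to PFS, and nothing in the SAP corrects it. The direction follows from the text; the size rests on the assumptions above. Pooled, it is probably modest: about 1 to 4 percentage points in DCR and 2 to 6 days in median PFS. In the low-dose rows the distortion could be severe, though on very few patients.

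Three stronger readings are not supported. One is a larger pooled effect: 15 low-dose patients all waiting 56 days and all escalating if progression-free would take DCR to 59% and median PFS to 72 days. That ignores the longer waits from levels 1 and 2 and the TP53 condition, and the ladder itself supports only about 9 patients in Regimen A at three per level. Another is a material effect on DCB, which is small or nil. The third is calling the DCR problem immortal time: DCR is a proportion, so the fault there is selection.

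**What to change.** In SAP 5.2 and Protocol 7.6, replace the first condition with: *Were assigned to a starting dose level of at least 0.8 mg/kg per infusion and received at least one dose of ALRN-6924.* The second half must stay: SAP 3.2.2 defines enrollment as having been dosed, but Protocol 7.6 has no such rule. State in SAP 3.1 that dose cohort means assigned starting dose. List the outcomes of patients escalated from lower levels separately, so that no observed activity is lost.

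The cost is a wording change in two places, one definition and one listing, with no new data and no change to dosing. A few patients may leave the set, and pooled DCR and PFS may look slightly less favourable.

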6. SUBJECT ACCOUNTING

6.1. SUBJECT DISPOSITION

The total number of subjects enrolled, treated, and discontinued from treatment will be summarized including reasons for discontinuation. Reasons for treatment discontinuation include:

- Adverse Event
- Objective Disease Progression
- Clinical Disease Progression
- Non-compliance
- Consent withdrawn
- Lost to follow-up
- Death
- Other

Inclusion/exclusion criteria that were not met will be listed by subject, including designation of whether a waiver was granted.

Important protocol deviations will be listed.

6.2. SUBJECT EVALUABILITY

Accounting for all enrolled subjects and their inclusion in analysis sets (Safety Population and the Efficacy Evaluable Population), along with reasons for exclusion from analysis sets, will be summarized.

7. DEMOGRAPHICS, OTHER BASELINE CHARACTERISTICS AND MEDICATIONS

7.1. DEMOGRAPHIC AND OTHER BASELINE CHARACTERISTICS

Age (years), height (cm), weight (kg), and BMI (kg/m^2) at baseline will be summarized descriptively. Gender, race, and ethnicity will be summarized by frequency counts. Age is calculated as follows (in years):

$(\text{date of informed consent for the full study} - \text{date of birth} + 1) / 365.25$

Body mass index is calculated based on weight and height at baseline.

7.2. GENERAL MEDICAL AND SURGICAL HISTORY

Medical history events will be coded using Medical Dictionary for Regulatory Activities (MedDRA) version 19.1 or later which will provide a System Organ Class (SOC) and preferred term (PT) for each relevant medical or surgical history reported by the investigator.

These data will be summarized by SOC and PT.

7.3. CANCER DIAGNOSIS AND PRIOR CANCER-DIRECTED THERAPIES

The following factors will be tabulated:

- P53 status
- The time from initial cancer diagnosis to the first dose of ALRN-6924 calculated as follows (in years):
 $(\text{date of first dose} - \text{diagnosis date} + 1) / 365.25$
- Prior radiation therapy (yes, no)

- Prior cancer surgery (yes, no)

7.4. PRIOR AND CONCOMITANT MEDICATIONS

Concomitant medications are defined as medications ongoing or stopped on or after the date of the first dose of ALRN-6924. Prior and concomitant medications will be coded with World Health Organization Drug Dictionary (WHO DDE) Enhanced B2 Format September 1, 2016 or later.

Concomitant medications will be summarized. The number and percentage of subjects using each medication will be displayed together with the number and percentage of subjects using at least 1 medication within each medication group and subgroup.

8. SAFETY ANALYSES

8.1. STUDY TREATMENT AND EXTENT OF EXPOSURE

The ALRN-6924 administration profile will be summarized with respect to treatment duration (Treatment duration (days) = last treatment date - first treatment date + 1), number of infusions, total ALRN-6924 dose received (mg), average dose per cycle, number of cycles, number of subjects with dose modification(s), and reason for dose modification(s).

8.2. DOSE-LIMITING TOXICITIES

The number and percent of subjects experiencing DLTs will be summarized by DLT category.

8.3. ADVERSE EVENTS

Treatment-emergent adverse events (TEAEs) are defined as AEs that are newly occurring or worsening on or after the date of the first dose of ALRN-6924. Reported AE terms will be coded using MedDRA version 19.1 or later.

The number and percent of subjects, and the number of events where relevant, will be summarized by SOC and PT for the following categories of TEAEs:

- All TEAEs
- Grade 3 or higher CTCAE grade TEAEs
- Related TEAEs defined as at least possibly related, as delineated by the investigator, or missing
- Serious TEAEs

- Serious related TEAEs
- TEAEs leading to discontinuation of study drug
- TEAEs leading to death

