Safety will be evaluated based on the incidence, severity, duration, causality, seriousness, and type of AE, and changes in the patient's physical examination, vital signs and clinical laboratory results. Investigators will use the NCI CTCAE version 4.03 to assess the severity of AEs. The immunogenicity of ALRN-6924 will be assessed by the measurement of anti-ALRN-6924 antibodies.

If the safety profile appears favorable, the study may be amended in the future to expand existing cohorts or subsets of existing cohorts, add cohorts to test additional cancer types or add cohorts to test other combination treatments with ALRN-6924.

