5.8 Dose and Schedule Adjustments for Toxicity

5.8.1 Dose Modifications – Phase 1 dose escalation (ALRN-6924 administered as single agent therapy)

In the event a Grade 4 AE considered related to ALRN-6924 is observed, the patient must be discontinued from study treatment. Exceptions include Grade 4 neutropenia lasting <3 days, and emesis, diarrhea or electrolyte abnormalities that resolve within 2 days on optimum treatment. For these exceptions, treatment may be delayed for up to 2 weeks to allow resolution of the toxicity (i.e., return to Grade ≤ 1 or baseline), followed by re-treatment at a reduced dose. Two dose reductions are permitted; a third dose reduction will require evidence of clinical benefit and approval by the Medical Monitor. Relevant labs should be repeated as medically indicated.

In the event a Grade 3 AE considered related to ALRN-6924 is observed (exceptions are Grade 3 fatigue, nausea, emesis, diarrhea or clinically insignificant electrolyte abnormalities that resolve within 2 days on optimum treatment), treatment may be delayed for up to 2 weeks to allow resolution of the toxicity, followed by re-treatment at a reduced dose. Two dose reductions are permitted, a third dose reduction will require evidence of clinical benefit and approval by the Medical Monitor. Relevant labs should be repeated as medically indicated.

Dose modifications for re-treatment following related Grade 3 and Grade 4 AEs (as permitted): patients will be re-treated at the preceding dose level (per Figure 9).

For other clinically significant AEs, treatment may be delayed by up to 2 weeks to allow for the resolution of AEs to an acceptable level, and may continue treatment at a reduced dose level as described above at the discretion of the Investigator in consultation with Sponsor's Medical Monitor. If a patient experiences multiple AEs, decisions on dosing delay or dose reduction will be based on the most severe AE. Any patient who experiences recurrent, clinically significant AE after one dose reduction may undergo one additional dose reduction. Patients who continue to experience clinically significant AEs after a 2-week delay or the maximum allowed number of dose reductions will be discontinued from the study.

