5.9.2 Definition of Dose-Limiting Toxicity

A DLT will be defined as any Grade ≥ 3 AE that is considered to be possibly, probably, or definitely related to the study drug, with the following exceptions: (1) for fatigue, nausea, emesis, diarrhea or mucositis, only Grade ≥ 3 AE that do not respond within 48 hours to standard supportive/pharmacological treatment will be considered DLT; (2) for electrolyte imbalances, only Grade ≥ 3 AE that do not respond to correction within 24 hours will be considered DLT; (3) for infusion reactions, only a Grade 3 reaction which caused hospitalization or Grade 4 will be considered a DLT. In addition, specific hematologic DLTs are defined as:

- Thrombocytopenia – Grade 4 of any duration, Grade 3 for ≥ 7 days, or Grade 3 associated with clinically significant bleeding
- Neutropenia – Grade 4 for ≥ 3 days, or any Grade ≥ 3 febrile neutropenia

The above criteria will be used to make individual patient determinations regarding dose reductions, interruptions or discontinuation throughout the course of the trial, but DLTs occurring during Cycle 1 will be used to inform safety and tolerability assessments for dose escalation decisions.

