7.3 Safety Analysis

The safety population will include all patients who have received at least one dose of ALRN-6924. Adverse events, vital sign measurements, clinical laboratory information and concomitant medication usage will be tabulated. All toxicities will be summarized by severity based on the NCI CTCAE version 4.03 and relationship to treatment. Serious adverse events will be listed separately. Graphical displays will be provided where useful in the interpretation of results. Statistical analyses will be descriptive in nature and will account for all dose levels and regimens studied.

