8.3 Recording of Adverse Events

Each AE should be recorded in standard medical terminology on the AE eCRF page. Whenever possible, the AE should be evaluated and reported as a diagnosis rather than as individual signs or symptoms. For example, cough, runny nose, sneezing, sore throat, and head congestion should be reported as 'upper respiratory infection'. If a definitive diagnosis is not possible, the individual signs and symptoms should be recorded. Dates of start (onset) and stop (recovery), action taken, and outcome will be recorded in the AE eCRF page.

An abnormal laboratory value will not be considered as an AE unless it is 1) assessed as clinically significant by the Investigator, 2) requires intervention, or 3) results in a delay, discontinuation or change in the dose of study treatment. A clinically significant abnormal laboratory value will not be considered an AE if it is determined to be related to the study condition or concomitant conditions, e.g., diabetes, of which the Investigator was previously aware and have not worsened. An abnormal laboratory value considered as an AE will be recorded on the AE page or module.

The Investigator will evaluate all AEs with regard to maximum intensity and relationship to study drug, as follows.

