8.3.1 Maximum Intensity

Maximum intensity should be assigned using one of the severity grades as outlined in the NCI CTCAE v4.03; if the AE is not specifically listed in CTCAE v4.03, use the following grades:

- Grade 1: mild
- Grade 2: moderate
- Grade 3: severe/disabling
- Grade 4: life-threatening
- Grade 5: death

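### SAP 8.3 summarizes adverse event severity only as one pooled, any-causality Grade 3 or higher table, which is coarser than the severity and relationship summary described in protocol 7.3

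*SAP*

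**What the plan says.** Protocol 7.3 states: "All toxicities will be summarized by severity based on the NCI CTCAE version 4.03 and relationship to treatment". Protocol 8.3 shows that both attributes are recorded for every event: "The Investigator will evaluate all AEs with regard to maximum intensity and relationship to study drug". Protocol 8.3.1 fixes the scale: "Maximum intensity should be assigned using one of the severity grades as outlined in the NCI CTCAE v4.03", with Grades 1 to 5 spelled out for events that CTCAE does not list. Protocol 3.2 adds: "Safety will be evaluated based on the incidence, severity, duration, causality, seriousness, and type of AE".

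SAP 8.3 lists seven TEAE categories, each tabulated by SOC and PT: all; Grade 3 or higher; related; serious; serious and related; leading to discontinuation; leading to death. The severity category is "Grade 3 or higher CTCAE grade TEAEs", with no causality restriction. The relationship category is "Related TEAEs defined as at least possibly related, as delineated by the investigator, or missing", with no grade.

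Three other SAP safety outputs are relevant. SAP 8.1 gives reasons for dose modification. SAP 8.2 counts DLTs by DLT category. SAP 8.4 gives Grade 3 and 4 laboratory abnormalities by grade. SAP 3.1 promises tables by dose cohort within regimen, by regimen overall and overall, with listings of all data in addition. SAP section 11 says that the plan rests on Amendment 6 and declares one addition, duration of clinical benefit.

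**The concern.** Safety and tolerability is a primary objective of Phase 1, and severity and causality are among the features on which the protocol says safety will be judged. A programmer who follows SAP 8.3 as written will produce a severity summary with one cut, at Grade 3, and a relationship summary with no cut at all. A reader of the report could not then see how related toxicity of a given type is distributed over the grades at each dose.

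The protocol itself acts on related events at several grade thresholds. A related Grade 2 or higher event ended the dose-doubling stage, with fatigue at DL-4A and neutropenia at DL-3B (5.7.1). Related toxicity above Grade 2 bars intra-patient escalation, with listed exceptions (5.7.3). Related Grade 3 and related Grade 4 events are handled by different rules (5.8.1). The planned TEAE tables do not show related events at these thresholds.

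**Working it through.** No figure in the plan has to be reproduced. The check counts the planned tables and sets them against the two attributes named in protocol 7.3.

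**1. Inventory of SAP 8.3.**
- Tables in total: 7.
- Using grade: 1 (Grade 3 or higher, any cause).
- Using relationship: 2 (related; serious related).
- By individual grade: 0.
- Combining grade with relationship: 0.

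**2. Severity bands that can be recovered, any cause.** Protocol 8.3.1 has 5 grades. Subtraction of patient counts within a PT gives:
- Grade 1–2 as worst grade = all − Grade 3 or higher.
- Grade 5 = leading to death (this treats death as outcome and Grade 5 as the same thing).
- Grade 3–4 = Grade 3 or higher − leading to death.

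That is about 3 bands out of 5. Grade 1 is not separated from Grade 2, nor Grade 3 from Grade 4.

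**3. Severity bands for related events.** The related table pools all 5 grades. The Grade 3 or higher table and the related table cannot be combined to recover the joint count. If *a* patients have a Grade 3 or higher event of some PT and *b* have a related event of that PT, the number with a related Grade 3 or higher event is at most min(*a*, *b*). From those two tables alone it can be as low as 0, because a patient may have an unrelated Grade 3 event and a related Grade 1 event of the same type.

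**4. What the other tables add.**
- Serious related TEAEs include related deaths and related life-threatening events (SAE definition, protocol 8.1.2).
- TEAEs leading to discontinuation should include many related Grade 4 events, because protocol 5.8.1 generally requires treatment to stop for them. This table does not identify relationship.
- DLTs are related by definition and mostly Grade 3 or higher.
- The laboratory table separates Grade 3 from Grade 4, but for laboratory abnormalities only and without relationship.
- The dose-modification summary gives reasons, not grades.

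**5. What no table captures.** Under protocol 5.9.2, for fatigue, nausea, emesis, diarrhea and mucositis, only Grade 3 or higher events that "do not respond within 48 hours to standard supportive/pharmacological treatment will be considered DLT". Protocol 5.8.1 says of its Grade 3 rule that the "exceptions are Grade 3 fatigue, nausea, emesis, diarrhea or clinically insignificant electrolyte abnormalities that resolve within 2 days on optimum treatment".
- Types with the 48-hour DLT exception: 5.
- Non-electrolyte types excepted from the Grade 3 dose-modification rule: 4 (all of the above but mucositis).
- In both lists: 4.

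A related, non-serious Grade 3 event of one of these 4 types that settles quickly need not appear in the DLT, serious or discontinuation tables, or in the dose-modification summary. It is counted once under Grade 3 or higher and once under related, but never as both together. The Grade 1 versus Grade 2 split is missing for every TEAE type.

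**6. After the fix.** Tables by maximum grade give 5 bands for all TEAEs and 5 for related TEAEs.

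**The case against.** The strongest reply is that protocol 7.3 asks for severity and relationship, and the SAP has a category for each. Section 7.3 does not say by individual grade, by maximum grade or severity crossed with relationship. Protocol 8.3 and 8.3.1 govern how events are recorded, not how tables are laid out, and protocol section 7 leaves full details to the SAP. This stands in part. A reader might infer that the SAP breaches an express requirement for a five-grade table crossed with relationship; the wording does not go that far. What remains is that 7.3 speaks of all toxicities by severity, and one cut at Grade 3 is a subset, not a summary of all of them by severity.

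Second, the SAP is based on Amendment 6, while the supplied protocol contains a cohort added per Amendment 7. A reader might infer that the SAP departed from the protocol in force when it was written. That cannot be shown, because the Amendment 6 text of 7.3 is not available. The mismatch is between the documents as supplied.

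Third, the serious related, discontinuation and DLT tables recover part of the related high-grade events. This is correct, and it narrows the gap to the residual in step 5 of the working. It would be wrong to say that related high-grade toxicity goes unreported.

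Fourth, the Stage 2 switch has already happened and its triggers are named in the protocol, so a Grade 2 count changes no later dose decision. This too is correct.

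Fifth, listings hold the data, and a hand count is easy within a cohort of 3 to 6 patients. But SAP 3.1 promises listings in addition to tables, and its pooled columns cover about 75 patients (SAP 2.2). A listing does not replace a summary on that scale.

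**Conclusion.** The point holds as a gap in descriptive reporting. SAP 8.3 gives one pooled, any-causality severity cut where the supplied protocol 7.3 describes a summary of all toxicities by severity and relationship, and SAP section 11 does not declare the difference. In size: 1 of 7 TEAE tables uses grade, 0 are by individual grade and 0 combine grade with relationship. About 3 of 5 severity bands are recoverable for all TEAEs, and the related table has a single band, with partial help from the serious related, discontinuation and DLT tables.

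A reader might infer that dose finding is compromised. The documents do not support that: escalation and the MTD rest on DLTs and on the Safety Review Committee's review of all available safety data. No estimate is biased and no data are lost.

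The conclusion rests on the current wording of 7.3, on reading SAP 8.3 as the full list of TEAE tables, and on counting TEAEs leading to death as Grade 5. No event rates are assumed. It is a cheap improvement worth making.

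**What to change.** In SAP 8.3 add two tables, each with the columns SAP 3.1 already promises (dose cohort within regimen, regimen overall, overall):

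1. All TEAEs by SOC, PT and maximum CTCAE grade.
2. Related TEAEs by SOC, PT and maximum CTCAE grade, using the SAP's existing definition of related.

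Patients with related events at worst Grade 2, and at worst Grade 3 or higher, can then be read from the second table. A separate related Grade 3 or higher table, or a Cycle 1 split, is optional and not called for by protocol 7.3. If the sponsor prefers to keep the present list, SAP section 11 should state the difference from protocol 7.3.

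The cost is a few lines of SAP text and two table shells. Maximum intensity and relationship are already recorded for every adverse event, so no new data are needed. The only downside is a longer set of safety tables.
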